14.2.2 Analysis of Secondary Endpoints

University of Washington Quality of Life questionnaire (UW-QOL): The UW-QOL consists of 12 single question domains focusing on current patient health and quality of life within the past 7 days. These domains have between 3 and 6 response options that are scaled evenly from 0 (worst) to 100 (best) according to the hierarchy of response. The domains are pain, appearance, activity, recreation, swallowing, chewing, speech, shoulder, taste, saliva, mood and anxiety; patient choice of up to three of these domains that have been the most important to them. There are also three global questions, one about how the patient feel relative to before they developed their cancer, one about their health-related QOL and one about their overall QOL. In regard to their overall QOL, patients are asked to consider not only physical & mental health, but also many other factors, such as family, friends, spirituality or personal leisure activities that were important to their enjoyment of life.

Brief Pain Inventory (BPI): The BPI allows patients to rate the severity of their pain and the degree to which their pain interferes with common dimensions of feeling and function.

Dermatology Life Quality Index (DLQI): The DLQI is a ten-question questionnaire designed to measure the health-related quality of life of adult patients suffering from a skin disease. Each question is scored from 0 to 3, giving a possible score range from 0 (meaning no impact of skin disease on quality of life) to 30 (meaning maximum impact on quality of life).

For all these QoL measures, descriptive statistics (mean, SD, median, and inter-quartile range) will be primarily used to summarize the scored scales at each scheduled assessment time point. Additionally, change from baseline in the domain scores at the time of each assessment will be summarized. Patients with an evaluable baseline score and at least one evaluable post baseline score during the treatment period will be included in the change from baseline analyses. Mixed effect model for repeated measures (MMRM) will be used to examine the change of QoL measures with time and treatment.

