In this respect, cetuximab appears to have a different toxicity profile than that of traditional chemotherapy such as cisplatin. The most commonly reported side effect is the development of skin reactions including macular, papular, and pustular rashes, xerosis, fissures, telangiectasias, and hyperpigmentation of the hair and nails (Bernier et al., 2008). The most frequent of these reactions is an acne-like rash that predominately appears in areas rich in sebaceous glands. The acne-like rash comprises itchy erythematous follicular papules that evolve into pustules. Other presentations include diffuse erythema with follicular papulopustules and telangiectasia, a seborrhoeic dermatitis-like rash or, occasionally, an edematous facial erythema. In the absence of radiation, the acne-like rash can be seen within a few days of the initiation of treatment and peaks 2–3 weeks after starting therapy (Bernier et al., 2008).

The effect on the skin during the combination of cetuximab and radiation is of considerable interest, as it might require special care to reduce symptoms and severity. It appears that radiation may delay the onset of the cetuximab-induced rash as it typically appears within irradiated fields 3–5 weeks after initiation of treatment (Bernier et al., 2008). There appears to be no obvious relationship between the severity of cetuximab-associated acne-like rash outside irradiated fields and the severity of radiation dermatitis. The aforementioned Phase III trial (Bonner JA et al., 2010) revealed no statistically significantly increase in the incidence or severity of radiation dermatitis compared with radiotherapy alone. The incidence of grade 3 radiation dermatitis was 18% with RT alone and 23% with RT with cetuximab ($p = 0.27$). There was a slight increase in the median duration of radiation dermatitis in the cetuximab arm (11.1 weeks) compared with the RT-alone arm (9.4 weeks).

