process. Its clinical utility in reducing oral mucositis was assessed prospectively and was recently discussed in a Cochrane review (Clarkson et al., 2010; Guatuum AP et al., 2012; Migliorati et al., 2013). Here, LLLT showed a reduction in severe mucositis when compared with the sham procedure (risk ratio: 5.28, 95% confidence interval: 2.30 to 12.13). While these studies support an improvement in oral mucositis with LLLT, the clinical experience addressing an improvement in cetuximab-induced rashes and radiation-dermatitis is limited. An Italian case series (Gobbo et al., 2011) reported that in 4 patients with metastatic colorectal cancer and two patients with HNSCC, LLLT reduced cetuximab-related skin toxicities. Here, patients were treated with two 8-minute long consecutive sessions/day over a 4-day treatment. Patients were evaluated weekly for up to 3 weeks and after 180 days. Follow-up evaluations including a questionnaire about the onset and progression of the acneiform rash and visual analog scales were reported. The authors reported that after the fourth session of LLLT, the patients showed a decrease in both cetuximab-related toxicity and visual analog scales, up to complete regression of the lesions in all treated areas (Gobbo et al., 2011). No adverse effects from treatment were reported. These findings suggest that LLLT may be an effective way of managing cetuximab- and radiation-induced skin toxicities. Herein we propose a pilot study to assess the efficacy of LLLT to mitigate and ameliorate the acneiform-rash, radiation dermatitis, and pain while assessing its impact on PR-QoL measures.

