6.0 Procedures Involved

6.1 Screening / Pre-treatment:

- Medical history
- Physical examination, including Karnofsky Performance Status and vital signs.
- Signed informed consent
- Subject body weight and height
- Quality of Life Assessments (UW QoL, BPI, DLQI)

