6.2 Evaluation during Treatment

- Patients will be treated with the 69 diode LED cluster probe. The wavelength utilized are both 660 nm and 850 nm. The average power density is 100 mW/cm² and the spot size is 0.2 cm². Treatment time is 60 seconds to each site. There are a minimum of nine treatment sites: (1) left forehead, (2) right forehead, (3) left upper cheek/malar region, (4) right upper cheek/malar region, (5) right lower cheek / trigeminal nerve mandibular division distribution, (6) left lower cheek / trigeminal nerve mandibular division distribution, (7) submental region, (8) left neck, (9) right neck. Patients will be pretreated with a minimum of 3 sessions over 7 days before starting radiotherapy. Patients will receive LLLT at least twice the week prior to initiation of radiation and then at least three times per week during the course of radiation treatment.

- Adverse Event Assessment (Grading of skin toxicity and mucositis by patient)
- Completion of patient reported DLQI during treatment week 5 and at end of treatment

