6.3 Evaluation following Treatment

- Patients will be seen in follow-up at least every three months in the first year following completion of treatment.
 - Observer reported mucositis and skin reaction every three months for one year
 - Patient reported QoL assessments (UQ QoL, BPI, DLQI) every three months for one year

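### The change-from-baseline rule requires an on-treatment score, but UW-QOL and BPI are never scheduled on treatment, so no patient qualifies for either

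*Combined protocol and SAP*

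**What the plan says.** Section 14.2.2 treats the three questionnaires together. Descriptive statistics at each time point are the main summary. The section then adds: "Additionally, change from baseline in the domain scores at the time of each assessment will be summarized". The next sentence defines who enters those analyses: "Patients with an evaluable baseline score and at least one evaluable post baseline score during the treatment period will be included".

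The collection schedule is in section 6:

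- Section 6.1, screening: "Quality of Life Assessments (UW QoL, BPI, DLQI", so all three instruments have a baseline.
- Section 6.2, during treatment: "Completion of patient reported DLQI during treatment week 5 and at end of treatment". No other questionnaire is listed there.
- Section 6.3, after treatment: "Patient reported QoL assessments (UQ QoL, BPI, DLQI) every three months for one year". The same section places these visits after treatment: "Patients will be seen in follow-up at least every three months in the first year following completion of treatment".

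No section defines the treatment period so as to include the follow-up year.

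**The concern.** The rule in 14.2.2 asks for something that section 6 does not collect. For UW-QOL and BPI, every post-baseline form falls after treatment, so no form can satisfy a requirement for an on-treatment score. The rule also conflicts with the sentence just before it, which promises change at each assessment; for these two instruments all such assessments are in follow-up.

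At stake is a planned analysis of all three secondary endpoints. As written, it cannot be produced for two of them, and for the third it leaves out patients with usable follow-up data. If the rule stays, whoever analyses the data must choose the analysis set after seeing the data.

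A related design point is separate from the contradiction. Section 3 says the study is meant to "assess the efficacy of LLLT to mitigate and ameliorate the acneiform-rash, radiation dermatitis, and pain while assessing its impact on PR-QoL measures", yet no BPI is scheduled at any time during treatment.

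**Working it through.** The plan gives no figure for the size of the change-from-baseline set, so there is none to reproduce on this point. Its only computed figures, the exact confidence intervals in section 14.3, concern the primary endpoint. They reproduce (maximum width 23.6%, stated as 24%) and have no bearing here.

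**Step 1. Count scheduled forms by period (sections 6.1 to 6.3).** Quarterly collection over one year is counted as 4 follow-up assessments. This is nominal, because visits are described as a minimum frequency.

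| Instrument | Baseline | On treatment | Follow-up |
|---|---|---|---|
| UW-QOL | 1 | 0 | 4 |
| BPI | 1 | 0 | 4 |
| DLQI | 1 | 2 | 4 |

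Both DLQI forms listed in section 6.2, including the one at the end of treatment, are counted as on treatment.

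**Step 2. Apply the rule to each instrument, with N = 75 (section 14.3).** A patient qualifies only with a baseline score and at least one on-treatment score.

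| Instrument | Maximum eligible, rule as written | Maximum eligible, any post-baseline score |
|---|---|---|
| UW-QOL | 0 of 75 | 75 of 75 |
| BPI | 0 of 75 | 75 of 75 |
| DLQI | 75 of 75 | 75 of 75 |

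These are upper bounds before missing data.

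**Step 3. Count the empty summaries.** Section 14.2.2 gives UW-QOL 12 domains: 12 × 4 follow-up visits = 48 change summaries, all empty. BPI change is empty at all 4 follow-up visits.

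**Step 4. DLQI patients lost.** A patient is dropped if both on-treatment forms are missing. Let *p* be the share of patients missing each form. The documents give no value, so *p* is assumed. If misses are independent, the expected loss is 75 × *p*². If the same patients miss both forms, it is 75 × *p*.

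| Assumed *p* | Independent misses | Same patients miss both |
|---|---|---|
| 10% | 75 × 0.01 = 0.75 | 75 × 0.10 = 7.5 |
| 20% | 75 × 0.04 = 3 | 75 × 0.20 = 15 |
| 30% | 75 × 0.09 = 6.75 | 75 × 0.30 = 22.5 |

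These patients would be excluded even if all 4 of their follow-up forms were complete.

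**The case against.** The strongest reply is that little is lost in practice. The study is descriptive, and the time-point summaries that the plan mainly relies on can still be produced, so baseline and follow-up means can be compared. The mixed model is described in its own sentence with no stated entry rule, so it may also survive. An analyst would probably infer the intent from the promise of change at each assessment and would not deliver empty tables. This stands as a limit on the consequence: what is certainly lost is the paired change summary. It does not make the written rule workable.

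A second reply is that the rule is worded for patients, not for instruments, so an on-treatment DLQI score might qualify a patient for all three. The text does not say so. That reading would also exclude patients with complete UW-QOL and BPI data who happened to miss the DLQI forms. Applying the rule to each instrument is the natural reading, and the count of zero depends on it.

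Third, the error may lie in the schedule: on-treatment UW-QOL and BPI may have been intended and left out of section 6.2. The documents do not settle this. A rule that accepts any scheduled post-baseline score works in either case.

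Fourth, for the DLQI the rule is at least compatible with its schedule, so requiring an on-treatment score could be a deliberate choice of analysis set. That is fair. The DLQI loss is a side effect whose size rests on assumed missingness, and the contradiction does not depend on it.

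**Conclusion.** The concern holds: the entry rule is wrong as written. Applied to each instrument, with follow-up taken as outside the treatment period as the headings of sections 6.2 and 6.3 indicate, it leaves the change-from-baseline analysis with no eligible patients for two of the three secondary endpoints. For the DLQI it removes from under 1 to about 22 of 75 patients, depending on assumed missingness of 10% to 30% per form and on how far the misses overlap.

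The primary endpoint, the sample size and the main descriptive quality-of-life summaries are not affected. Whether the mixed model is affected cannot be determined, because its analysis set is not stated. The point should be fixed before analysis, but it does not threaten the study's main result.

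**What to change.** In section 14.2.2, replace the requirement for an on-treatment score with *at least one evaluable post-baseline score at any scheduled assessment*, and state that it applies to each instrument separately. This changes one sentence of the analysis plan. It needs no new data, visits or patients, and has no cost.

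A separate option, not needed to remove the contradiction, is to collect BPI and UW-QOL alongside the DLQI at the two time points in section 6.2, so that pain and head-and-neck quality of life are also measured during treatment. The cost is patient burden: two more questionnaires at two contacts where the DLQI is already completed. UW-QOL has 12 domain items, a choice of the most important domains and 3 global questions. The documents do not give the length of the BPI.

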1.0 Study Summary

Study Title	Utilization of Low Level Laser Therapy (LLLT) for Radiation-Induced Dermatitis in Patients with Head and Neck Squamous Cell Carcinoma (HNSCC)
Study Design	Single-arm, Phase I/II
Primary Objective/Endpoint	
Assess the safety and efficacy of low level laser therapy (LLLT) in mitigating radiation-induced dermatitis in patients undergoing radiation therapy for head and neck squamous cell carcinoma (HNSCC)
 
Endpoint: Documented Grade 3 or higher Adverse Events as per CTCAE v4.0

Secondary Objective(s)/Endpoints	
assessment of patient-reported quality of life data, pain parameters and dermatologic quality of life responses
 
Endpoints:
 
 • quality of life data measured using the University of Washington Quality of Life Questionnaire (UW-QOL) • pain parameters assessed using Brief Pain Inventory (BPI) • dermatologic quality of life responses measured using the Dermatology Life Quality Index (DLQI)
Research Intervention(s)/Investigational Agent(s)	THOR Laser system
IND/IDE #	N/A
Study Population	patients with histologically proven squamous cell carcinoma of the oral cavity, oropharynx, hypopharynx or larynx who are candidates for either definitive or adjuvant therapy consisting of a chemotherapy regimen and concurrent radiation therap
Sample Size	75 planned
Study Duration for individual participants	15 months

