7.0 Study Timelines

- The expected duration of an individual subject's participation is approximately 15 months.

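### Applied per instrument, the change-from-baseline rule in Section 14.2.2 leaves no patient scheduled to qualify for UW-QOL or BPI, and the MMRM's treatment term is undefined

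*Combined protocol and SAP*

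**What the plan says.** Section 1.0 gives the design as "Single-arm, Phase I/II". Section 6.2 schedules every patient for low level laser therapy (LLLT), and Section 12.0 names only published historical toxicity reports as a comparator.

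The quality-of-life schedule is spread over three subsections:

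- **6.1, screening:** all three instruments.
- **6.2, during treatment:** "Completion of patient reported DLQI during treatment week 5 and at end of treatment". Neither UW-QOL nor BPI is listed.
- **6.3, following treatment:** "Patient reported QoL assessments (UQ QoL, BPI, DLQI) every three months for one year". The visits themselves are placed after therapy: "Patients will be seen in follow-up at least every three months in the first year following completion of treatment".

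Section 14.2.2 makes descriptive statistics at each scheduled time point the main analysis for all three instruments and adds change from baseline at each assessment. It then restricts that second analysis to patients who have a baseline score and "at least one evaluable post baseline score during the treatment period will be included in the change from baseline analyses". It closes with: "Mixed effect model for repeated measures (MMRM) will be used to examine the change of QoL measures with time and treatment". It does not define the treatment period, does not say whether the restriction works per instrument or per patient, and gives no levels, reference or contrast for treatment.

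**The concern.** The restriction asks for an on-treatment score that the schedule does not collect for two of the three secondary instruments. An analyst who applies it literally has an empty change-from-baseline analysis for UW-QOL and BPI. One who does not must choose the population after the data are in.

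The MMRM sentence leaves a second choice open. Depending on how treatment is coded, the term cannot be fitted, or it can be fitted but picks up the expected course of chemoradiation toxicity and recovery, or it describes a between-patient factor that the plan never names. The second case carries most risk, because the software returns a coefficient that could be read as an effect of LLLT.

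**Working it through.** The plan gives no quality-of-life figure to reproduce. Its only calculation, the exact confidence intervals in Section 14.3, concerns the adverse event rate and does not bear on this point.

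**Step 1. Scheduled forms against the rule.** Inputs: 75 patients (14.3) and the schedule in 6.1 to 6.3. I take three-monthly for one year to mean months 3, 6, 9 and 12. Full completion is assumed.

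| Instrument | Screening | During treatment | Follow-up | Scheduled to qualify as written | If any post-baseline score counts |
|---|---|---|---|---|---|
| UW-QOL | 1 | 0 | 4 | 0 of 75 | 75 of 75 |
| BPI | 1 | 0 | 4 | 0 of 75 | 75 of 75 |
| DLQI | 1 | 2 | 4 | 75 of 75 | 75 of 75 |

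Follow-up forms outside the rule: 75 × 4 = 300 each for UW-QOL and BPI, 600 together. They are lost only to the change-from-baseline analysis; all stay in the by-visit summaries.

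For DLQI, a patient who misses both on-treatment forms is dropped despite up to four later scores. The plan gives no missing-data rate. If 10% missed both, that is 75 × 0.10 = 7.5 patients; if 20%, 75 × 0.20 = 15.

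**Step 2. Can a treatment term be estimated?** I compared the rank of the fixed-effects matrix with its number of columns for 75 patients who all follow the schedule. There are 6 post-baseline visits for DLQI and 4 for UW-QOL and BPI. A rank below the number of columns means the term cannot be separated from the others.

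| Coding of treatment | Time | DLQI | UW-QOL, BPI |
|---|---|---|---|
| None (time only) | categorical visit | 6 of 6 | 4 of 4 |
| LLLT, the same for everyone | categorical visit | 6 of 7 | 4 of 5 |
| LLLT, the same for everyone | linear | 2 of 3 | 2 of 3 |
| On/off LLLT (on at week 5 and end of treatment) | categorical visit | 6 of 7 | 4 of 5 |
| On/off LLLT | linear | 3 of 3 | 2 of 3 |
| Pre/post LLLT, baseline kept as a response | categorical visit | 7 of 8 | 5 of 6 |
| Pre/post LLLT, baseline kept as a response | linear | 3 of 3 | 3 of 3 |

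Two departures make a term estimable with categorical visit. If one of the 75 patients is off LLLT at both on-treatment visits (Section 9.0 allows therapy to be discontinued), the DLQI on/off term reaches 7 of 7. A two-level between-patient factor with its visit interaction gives 12 of 12 for DLQI. Neither is a comparison of LLLT with no LLLT in comparable patients.

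**Step 3. What an estimable on/off term would measure.** Suppose the true LLLT effect is zero and DLQI rises by d points on treatment because of chemoradiation. I regressed the six visit means on an intercept, linear week and the on/off indicator, with follow-up visits 13 weeks apart and a radiotherapy course of 6 to 8 weeks (assumed).

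- Recovery complete by month 3, means (1, 1, 0, 0, 0, 0)d: on/off coefficient 1.00d.
- Gradual recovery, means (1, 1, 0.5, 0.25, 0.1, 0)d: 0.369d, 0.363d and 0.358d for 6, 7 and 8 weeks.

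The recovery patterns are illustrations, not data. They show that a nonzero coefficient can arise with no LLLT effect at all.

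**The case against.** **The rule can be read so that it works.** It is worded about patients and does not say that the on-treatment score must come from the same instrument. An on-treatment DLQI could then qualify a patient for all three, giving 75 of 75. Likewise, if the treatment period meant the whole of each subject's time on study (Section 7.0: "participation is approximately 15 months"), the follow-up forms would count. Both readings are possible, so the count of zero is conditional. The text states neither. Section 6.3 places follow-up after treatment by its heading and its wording, and under the first reading a patient missing both DLQI forms would lose complete UW-QOL and BPI data.

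**The plan promises no LLLT effect.** This stands. A reader might infer that the MMRM sentence commits the trial to an effect that its design cannot deliver. The sentence names no contrast, and Section 14.3 says the study is not for hypothesis testing. Patients may have definitive or adjuvant therapy (1.0), and LLLT sessions are set as minimum numbers (6.2), so treatment may mean a between-patient factor that can be fitted. The defect is an undefined term.

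**The schedule, not the rule, may be at fault.** UW-QOL and BPI may have been left out of Section 6.2 by mistake. The documents do not settle this. The sponsor must reconcile the sections, and changing the rule is the route that needs no extra data collection.

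**Conclusion.** The point holds in a limited form. Sections 14.2.2 and 6.1 to 6.3 conflict. On the plain per-instrument reading, with follow-up outside the treatment period, 0 of 75 patients are scheduled to qualify for change from baseline on two of the three secondary instruments, although the same section commits to that summary at each assessment. For DLQI the rule also discards patients who have only follow-up scores.

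Separately, treatment in the MMRM is undefined. No LLLT-versus-none effect can be estimated from one arm. An on/off or pre/post term is aliased with categorical visit under full adherence. Where it can be estimated, it is confounded with chemoradiation toxicity and recovery, or with the reason for stopping.

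A reader might go further and conclude that the whole quality-of-life plan fails. The documents do not support that: the by-visit summaries that the plan treats as primary, the DLQI change from baseline for patients with an on-treatment score, and a time-only MMRM all work. The primary endpoint and the sample size of 75 are untouched. This should be fixed, but it concerns secondary descriptive analyses only.

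Confidence is high on the schedule and on the absence of an LLLT contrast. It is moderate on what the authors meant by treatment and treatment period.

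**What to change.** 1. Reconcile Section 14.2.2 with Sections 6.1 to 6.3 by rewording the rule to require an evaluable baseline score and at least one evaluable post-baseline score on that instrument at any scheduled visit.
2. In the MMRM sentence, replace the reference to time and treatment with change over time. Report mean change and its 95% CI by visit, and state that time trends are not attributed to LLLT. If a between-patient factor was meant, name it and its levels, and label the result a non-randomised descriptive association.

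The cost is two wording changes in one section, with no new visits, patients or forms. If the sponsor intended UW-QOL and BPI to be collected during treatment, Section 6.2 would have to change as well, and that would add forms.
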